#### **10.2.3.2 Meal Schedule**

Water will be allowed ad libitum at all times. Other fluids may be given as part of meals and snacks but will be restricted at all other times throughout the confinement period.

At the CRU, standard meals and snacks will be provided at appropriate times. When confined in the CRU, subjects will be required to fast from all food and drink except water between meals and snacks.

Each meal and/or snack served at the CRU will be standardized and will be similar in caloric content and composition. The same menu and meal schedule will be administered uniformly for all subjects for all cohorts.

Subjects will be required to fast for at least 8 hours before the clinical laboratory tests at screening and before the clinical laboratory tests at other scheduled times (except for the 8-hour time point). However, in case of dropouts or rechecks, subjects may not have fasted for 8 hours before the serum chemistry sample is taken.

#### **10.2.3.3 Day 29 Study Procedures**

Before leaving the CRU facility on Day 29, all subjects will undergo all study procedures listed on Day 29 in the Study Events Flow Chart (see [Section 6](#)). In the event that aPTT values did not return within  $\pm$ 10% of the baseline value or the normal range, sampling will continue every 7 days ( $\pm$ 2 days), as indicated in the Study Events Flow Chart (see [Section 6](#)), until  $\pm$ 10% of the baseline value or the normal range is reached.

#### **10.2.4 Follow-up Visit**

Subjects for whom aPTT value reaches  $\pm 10\%$  of the baseline value or within the normal range by Day 29 will return to the CRU for the FU visit on Day 36 to perform scheduled follow-up procedures and to determine if any AE has occurred since the last study visit.

Subjects for whom aPTT did not reach  $\pm 10\%$  of the baseline value or within the normal range on Day 29, will return every 7 days ( $\pm 2$  days) until aPTT reach  $\pm 10\%$  of the baseline value or within the normal range and for the FU visit (i.e., follow-up procedures and AE evaluation) 7 days ( $\pm 2$  days) after it was reached. If aPTT values remain elevated past Day 29, an additional ADA sample collection will occur at the FU visit.

Subjects who terminate the study early will be asked to continue aPTT monitoring as scheduled in the Study Events Flow Chart ([Section 6](#)) until it reaches  $\pm 10\%$  of the baseline value or within the normal range. They will return to the CRU approximately 7 days ( $\pm 2$  days) after aPTT reaches  $\pm 10\%$  of the baseline value or within normal range for the FU visit to perform scheduled follow-up procedures, and to determine if any AE has occurred since the last study visit. They will also be asked to return on Days 15 and 29 to collect the ADA samples.

The follow-up procedures are listed in the Study Events Flow Chart (see [Section 6](#)).

#### **10.2.5 Scheduled End of Study**

The end of the study is scheduled after completion of the evaluations in the 4 cohorts or after dose-limiting clinical safety endpoints have been reached to preclude further increases of dose.

### **10.3 Selection of Study Population**

#### **10.3.1 Number of Subjects**

The study is planned to enroll up to 21 subjects in 4 cohorts. The first cohort will enroll 6 subjects; 4 subjects randomized to receive the active drug and 2 subjects to receive the placebo. The remaining 3 cohorts will enroll 5 subjects; 4 subjects randomized to receive the active drug and 1 subject to receive the placebo per the randomization. In each cohort, at least 30% of the subjects must be of a race/ethnicity minority group. An attempt will be made to include at least 2 females per cohort.

Two sentinel subjects will be dosed (one placebo, one active) in Cohort 1 and data will be collected through Day 8 as described in the Study Events Flow Chart ([Section 6](#)). The next subject in the cohort will be dosed after evaluation of the sentinel subjects' Day 8 safety data. Each subject following these sentinel subjects will be dosed with an interval of 24-hour between subjects

Subjects in Cohorts 2, 3, and 4 will be dosed at an interval of 24 hours between subjects.

Additional subjects (N = 5 subjects per cohort; 4 active and 1 placebo) may be enrolled if it is deemed appropriate by the SRC to repeat a dose level or to study an interim dose level (lower than those planned) in a new cohort of subjects.

### 10.3.2 Inclusion Criteria

Subjects must fulfill all of the following inclusion criteria to be eligible for participation in the study, unless otherwise specified:

1. Healthy adult male and/or female (non-childbearing potential only), 18 to 48 years of age, inclusive, at screening.
2. Continuous non-smoker who has not used nicotine-containing products for at least 3 months prior to dosing and throughout the study.
3. Body mass index (BMI)  $\geq 19$  and  $\leq 29.0$  ( $\text{kg}/\text{m}^2$ ) and weight between 50 and 125 kg (inclusive) at screening.
4. Medically healthy with no clinically significant medical history, physical examination, laboratory profiles, vital signs or ECGs, as deemed by the PI or designee.
5. Aspartate aminotransferase (AST), alanine aminotransferase (ALT), alkaline phosphatase (ALP), lactate dehydrogenase (LDH), blood urea nitrogen (BUN), creatinine must be between the lower limit of normal (LLN; or up to 15% below LLN as not indicative of hepatic or renal disease in healthy subjects) and the upper limit of normal, inclusive, as indicated in [Appendix 1](#) at screening and check-in.
6. aPTT, PT/INR, and platelets, must be within the limits of normal, inclusive, as indicated in [Appendix 1](#) at screening and check-in.
7. Bleeding time must be between 2 to 8 minutes, inclusive, at check-in.
8. For a female of non-childbearing potential: must have undergone one of the following sterilization procedures at least 6 months prior to dosing:
  - hysteroscopic sterilization;
  - bilateral tubal ligation or bilateral salpingectomy;
  - hysterectomy;
  - bilateral oophorectomy;or be postmenopausal with amenorrhea for at least 1 year prior to dosing and follicle-stimulating hormone (FSH) serum levels consistent with postmenopausal status as per PI or designee judgment.

9. A non-vasectomized male subject whose sexual partner is sterile or was advised to use one of the following during the course of the study (or prior to study as specified) and for 90 days following dosing:

- Abstain from sexual intercourse;

- An intrauterine device with spermicide;
- A physical barrier method (e.g., male or female condom, contraceptive sponge, diaphragm, cervical cap) with spermicide;
- An intravaginal system (e.g., NuvaRing®) for at least 3 months prior to dosing;
- An oral, implantable, transdermal, or injectable hormonal contraceptive for at least 3 months prior to dosing.

No restrictions are required for a vasectomized male provided his vasectomy has been performed 4 months or more prior to dosing. A male who has been vasectomized less than 4 months prior to dosing must follow the same restrictions as a non-vasectomized male.

10. If male, must agree to not donate sperm from dosing until 90 days after dosing.
11. Understands the study procedures in the informed consent form (ICF), and be willing and able to comply with the protocol.

### **10.3.3 Exclusion Criteria**

Subjects will be excluded from the study if there is evidence of any of the following criteria at screening or check-in, as appropriate.

1. Subject is mentally or legally incapacitated or has significant emotional problems at the time of the screening visit or expected during the conduct of the study.
2. History or presence of clinically significant medical or psychiatric condition or disease in the opinion of the PI or designee.
3. History of any illness that, in the opinion of the PI or designee, might confound the results of the study or poses an additional risk to the subject by their participation in the study.
4. History or presence of drug abuse within the last 2 years prior to dosing.
5. History of alcoholism within the last 2 years prior to dosing or a current history of imbibing 3 or more units of alcohol per day (1 unit is equivalent to 150 mL of wine or 360 mL of beer or 45 mL of 45% alcohol).
6. History or presence of hypersensitivity or idiosyncratic reaction to the study drug, any ingredients of the study drug, or related compounds.
7. History of a clinically significant allergy of any kind including a history of allergic or hypersensitivity reactions to any drugs.

8. History or presence of:

- Bleeding disorder(s) and/or at risk of bleeding, including relevant familial history;
- Clinically significant anemia, in the opinion of the PI or designee;
- Thromboembolic disease;
- Bleeding in the gastrointestinal tract or central nervous system.

9. Allergy to rodents.

10. Had a minor surgery or major physical injury less than 4 weeks or major surgery less than 12 weeks prior to screening.

11. Was hospitalized within 2 months of dosing, unless deemed acceptable by the PI or designee.

12. Female subjects of childbearing potential.

13. Female subjects who are pregnant or lactating.

14. Positive urine drug or alcohol results at screening or check-in.

15. Positive results at screening for human immunodeficiency virus (HIV), hepatitis B surface antigen (HBsAg), or hepatitis C antibodies (HCV).

16. Seated blood pressure is less than 90/40 mmHg or greater than 140/90 mmHg at screening.

17. Seated heart rate is lower than 40 bpm or higher than 100 bpm at screening.

18. QTcF interval is >450 msec (males) or >460 msec (females) or has ECG findings deemed abnormal with clinical significance by the PI or designee at screening.

19. Hemoglobin value of less than 11.5 g/dL for females and 13.0 g/dL for males, at screening or check-in.

20. Unable to refrain from or anticipates the use of:

- Any prescription medications, non-prescription medications, herbal remedies, or vitamin supplements beginning approximately 14 days prior to dosing and throughout the study. Acetaminophen (up to 2 g per 24 hour period) may be permitted during the study and will be documented.
- Any anticoagulants (i.e., warfarin, Low Molecular Weight Heparin), coagulants, anti-platelet (e.g., clopidogrel), nonsteroidal anti-inflammatory drugs and/or

acetylsalicylic acid beginning approximately 28 days prior to dosing and throughout the study. Appropriate sources will be consulted by the PI or designee to confirm lack of PK/PD interaction with study drug.

- Any investigational drugs or biologics beginning approximately 30 days prior to dosing and throughout the study.
- Any biologics developed from chinese hamster ovary cell cultures in their life time.

21. Has been on a diet incompatible with the on-study diet, in the opinion of the PI or designee, within the 28 days prior to dosing and throughout the study.

22. Donation of blood or significant blood loss within 56 days prior to dosing.

23. Plasma donation within 7 days prior to dosing.

24. Strenuous exercise/physical activity which could cause muscle aches or injury, including contact sports at any time from 72 hours before dosing until completion of the study.

25. Participation in another clinical study within 30 days prior to dosing. The 30-day window will be derived from the date of the last blood collection or dosing, whichever is later, in the previous study to Day 1 of the current study.

26. Presence of any scars, or tattoos which may obscure the injection site, as deemed by PI or designee.

27. Any condition or circumstance, in the opinion of the PI or designee, which may make the subject unlikely to complete the study or comply with study procedures and requirements, or may pose a risk to the subject's safety.

#### **10.3.4 Early Termination of Subjects from the Study**

Subject participation in this trial may be discontinued for any of the following reasons:

1. Occurrence of any medical condition or circumstance that exposes the subject to substantial risk and/or does not allow the subject to adhere to the requirements of the protocol.
2. Any SAE, clinically significant AE, severe laboratory abnormality, intercurrent illness, or other medical condition that indicates to the PI that continued participation is not in the best interest of the subject.
3. Subject's decision to withdraw.
4. Requirement of prohibited concomitant medication.
5. Subject failure to comply with protocol requirements or study related procedures.

6. Termination of the study by the Sponsor, FDA, Celerion, SRC, or other regulatory authorities.

The clinical report will include reason(s) for subject withdrawals as well as details relevant to the subject withdrawal. If a subject is withdrawn from the trial prior to study completion, the subject will undergo all procedures scheduled for early termination as the situation allows (see [Section 10.2.3.3](#)). Any subject withdrawn due to an AE (whether serious or non-serious) or clinically significant abnormal laboratory test values will be evaluated by the PI or a monitoring physician and will be treated and/or followed up until the symptoms or values return to normal or acceptable levels, as judged by the PI or designee.

Subjects withdrawn may be replaced at the Sponsor's discretion.

### **10.3.5 Study Restrictions**

#### **10.3.5.1 Prohibitions and Concomitant Therapy**

Consumption of foods and beverages containing the following substances will be prohibited as indicated:

- Xanthines/caffeine: 48 hours before dosing and throughout the period of sample collection (small amounts of caffeine derived from normal foodstuffs e.g., 250 mL/8 oz. decaffeinated coffee or other decaffeinated beverage, per day, with the exception of espresso; 45 g/1.5 oz chocolate bar, per day, would not be considered a deviation to this restriction)
- Alcohol: 48 hours before dosing and throughout the period of sample collection;

Concomitant therapies will be prohibited as listed in the exclusion criteria in [Section 10.3.3](#).

During the study, acetaminophen (up to 2 g per 24 hours) may be administered at the discretion of the PI or designee.

If deviations occur, the PI or designee will decide on a case-by-case basis whether the subject may continue participation in the study based on the time the study medication was administered and its pharmacology.

All medications taken by subjects during the course of the study will be recorded.

#### **10.3.5.2 Activity**

Subjects will remain ambulatory or seated upright for the first 4 hours following study medication administration, except when they are supine or semi-reclined for study procedures. However, should AEs occur at any time, subjects may be placed in an appropriate position or will be permitted to lie down on their side.

Subjects will be instructed to refrain from strenuous exercise/physical activity which could cause muscle aches or injury, including contact sports at any time from 72 hours before to dosing until completion of the study.

## 10.4 Treatments

### 10.4.1 Treatments Administered

A separate dosing manual will detail the drug preparation and treatment administration to be followed for this study.

#### 10.4.1.1 Drug Administration

Xisomab 3G3 will be supplied as sterile powder for injection via the IV route, upon reconstitution.

Matching placebo will be supplied as sterile powder for injection via IV route, upon reconstitution.

An unblinded pharmacist will be responsible for providing xisomab 3G3 or placebo to the blinded study personnel for administration as per the randomization scheme. All doses will be administered by a hand pushed IV infusion into a peripheral vein. The time of infusion for each dose level is outlined below:

Dose Level	Manual Push time
Cohort 1: 0.1 mg/kg	~1 minute
Cohort 2: 0.5 mg/kg	~2 minutes
Cohort 3: 2 mg/kg	~3 minutes
Cohort 4: 5 mg/kg	~5 minutes

Dosing will be done while subjects are supine in bed.

The subject weight recorded at check-in will be used to calculate the study drug dose.

The time at which the infusion is started and stopped must be recorded.

Should the need arise to change the infusion rate (i.e., due to an AE), changes to the infusion rate and the times at which those changes are made will be documented.

Hour 0 will correspond to the start of the infusion.

#### 10.4.1.2 Planned Dose Levels

The planned dose levels are as follows:

Cohort 1: 0.1 mg/kg xisomab 3G3 or matching placebo

Cohort 2: 0.5 mg/kg xisomab 3G3 or matching placebo

Cohort 3: 2 mg/kg xisomab 3G3 or matching placebo

Cohort 4: 5 mg/kg xisomab 3G3 or matching placebo

Two sentinel subjects will be dosed (one placebo, one active) in Cohort 1 and data will be collected through Day 8 as described in the Study Events Flow Chart (Section 6). The next subject in the cohort will be dosed after evaluation of the sentinel subjects' Day 8 safety data. Each subject following these sentinel subjects will be dosed with an interval of 24-hour between subjects.

In Cohorts 2, 3, and 4, subjects will be dosed at an interval of 24 hours between subjects.

#### **10.4.1.3 Additional Dose Levels**

Additional subjects (N = 5 subjects per cohort; 4 active and 1 placebo) may be enrolled if it is deemed appropriate by the SRC to repeat a dose level or to study an interim dose level (lower than those planned) in a new cohort of subjects.

The IRB should be immediately notified of this revised approach.

#### **10.4.1.4 Dose Escalation and Stopping Rules**

A decision to proceed to the next higher dose administration will be made by SRC comprised of, but not limited to, the medical monitor, PI, and Sponsor Representative.

The SRC will review all pertinent blinded safety/tolerability data (e.g., physical examinations, ECGs, vital signs, clinical laboratory tests, and AEs) using all available data through Study Day 29 collected from all subjects dosed in the current cohort and from all subjects from previous cohorts to base dose escalation decision. At least 4 out of 5 subjects from the current cohort must complete scheduled safety procedures up to Day 29 prior to the decision to proceed to the next higher dosing cohort.

The safety data evaluation conducted by the SRC will be documented with the timing, recommendations, and decisions made by the SRC.

The maximum tolerated dose (MTD) will be considered as the last dose level before the dose level at which dose escalation is discontinued.

The SRC will make one of the following determinations:

1. To continue with the study as planned.
2. To continue with the study and add additional safety evaluations.
3. To stop the study or to continue with the study by adjusting to an intermediate dose between the current dose and the previous lower dose, if :
  - a. At least 1 subject has a SAE or visit to the emergency room regardless of relatedness to the study drug, except SAEs that are clearly and incontrovertibly due to extraneous causes (see [Section 11.1.9.4](#)).
  - b. At least 25% of subjects in a cohort experience a grade  $\geq 2$  AE.

Cohorts will be staggered to allow sufficient time for adequate review of safety and tolerability from the prior cohort.

PK data from a cohort may be used to guide the dose-escalation decision.

When applicable, a written statement fully documenting the reasons for study termination will be provided to the IRB.

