#### 10.1.1 Confinement, Return Visits, and Follow-Up

Subjects will be housed on Day -1, at the time indicated by the CRU, until after the 24-hour blood draw and/or study procedures. Subjects will only be discharged if the prothrombin time (PT)/international normalized ratio (INR) values are  $\leq$  3.5 and judged not clinically significant by the PI or designee. Subject will need to return to the CRU at least 2 days after discharge to confirm the PT/INR values.

Subjects will return for study procedures as indicated in the Study Events Flow Chart ([Section 6](#)). At all times, a subject may be required to remain at the CRU for longer at the discretion of the PI or designee.

Subjects for whom aPTT value reaches  $\pm$ 10% of the baseline value or within the normal range by Day 29, will return to the CRU for the FU visit on Day 36 to perform scheduled

follow-up procedures and to determine if any AE has occurred since the last study visit.

Subjects for whom aPTT did not reach  $\pm 10\%$  of the baseline value or within the normal range on Day 29, will return every 7 days ( $\pm 2$  days) until aPTT reach  $\pm 10\%$  of the baseline value or within the normal range and for the FU visit (i.e., follow-up procedures and AE evaluation) 7 days ( $\pm 2$  days) after it was reached. If aPTT values remain elevated past Day 29, an additional ADA sample collection will occur at the FU visit.

Subjects who terminate the study early will be asked to continue aPTT monitoring as scheduled in the Study Events Flow Chart ([Section 6](#)) until it reaches  $\pm 10\%$  of the baseline value or within the normal range. They will return to the CRU approximately 7 days ( $\pm 2$  days) after aPTT reaches  $\pm 10\%$  of the baseline value or within normal range for the FU visit to perform scheduled follow-up procedures and to determine if any AE has occurred since the last study visit. They will also be asked to return on Days 15 and 29 to collect the ADA samples.

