#### **10.4.4.2 Procedures for Breaking the Blind Prior to Study Completion**

One set of sealed envelopes containing the randomization code will be supplied to the PI or designee at the start of the study.

Breaking of the blind is expressly forbidden except in the event of a medical emergency where the identity of the drug must be known in order to properly treat the subject, or in the event of a safety interim analysis at the request of the sponsor (see [Section 10.4.4.3](#)).

In the event of a medical emergency, it is requested that the PI or designee make every effort to contact the Study Monitor or designee prior to breaking the blind. If breaking the blind is required because of a medical emergency, the treatment identity would be revealed by the PI or designee, for that subject only. In the event that the emergency is one, in which it appears that the other subjects may be at imminent risk, the blind may be broken for all subjects dosed at that dose level. The unblinding will be properly documented in the study file.

In all cases where the code is broken, the PI or designee should record the date and reason for code breaking.

At the end of the study, envelopes will be retained or destroyed according to site procedures unless specified otherwise by the Sponsor.

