#### **10.4.4.3 Interim Analysis**

##### Safety:

All available blinded safety data will be reviewed by the SRC prior to dose escalation.

At the Sponsor's request, unblinded safety tables, figures, and data listings may be presented to the sponsor's medical expert and head of regulatory for the purposes of planning the next initial Phase 2 studies prior to database lock. These interim analyses will be performed on data that will be edit-checked and monitored.

A safety programmer and a biostatistician at Celerion who are not involved with the present study will be unblinded to prepare unblinded safety tables, figures, and data listings. All the personnel related to the present study will remain blinded.

Pharmacokinetics:

Preliminary PK analysis may be performed to evaluate the sampling time points as the study progresses and to guide the dose escalation decision. In such a case, interim PK analysis will not use the actual subject numbers in order to avoid breaking the blind.

Pharmacodynamics:

Preliminary PD analysis may be performed to evaluate the sampling time points as the study progresses and to guide the dose escalation decision. In such a case, interim PD analysis will not use the actual subject numbers in order to avoid breaking the blind.

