## 11. STUDY PROCEDURES

### 11.1 Safety Assessments

The Study Events Flow Chart ([Section 6](#)) summarizes the clinical procedures to be performed at each visit. Individual clinical procedures are described in detail below. Additional evaluations/testing may be deemed necessary by the PI or designee and/or the Sponsor for reasons related to subject safety.

For this study, the primary assessment is the safety and tolerability. Safety will be determined by evaluating physical examinations, vital signs, ECGs, clinical laboratory parameters, including but not limited to, hematology, serum chemistry profile, coagulation, urinalysis, injection site reaction, immunogenicity, and AEs as outlined in the Study Events Flow Chart ([Section 6](#)).

Any nonscheduled procedures required for urgent evaluation of safety concerns take precedence over all routine scheduled procedures.

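### After an SAE or emergency room visit, nothing requires a dosing hold or Safety Review Committee review before the next subject in the same cohort is dosed

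*Protocol*

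**What the plan says.** Protocol 10.4.1.4 gives the SRC the decision to move to the next higher dose and lists the determinations it can make. The third is "To stop the study or to continue with the study by adjusting to an intermediate dose between the current dose and the previous lower dose". Criterion 3a, one of its two grounds, is met when "At least 1 subject has a SAE or visit to the emergency room regardless of relatedness to the study drug". The only exception is for SAEs that plainly have an extraneous cause. Section 10.4.4.3 places the committee's review at the same point: "All available blinded safety data will be reviewed by the SRC prior to dose escalation". Before the committee can go up a level, at least 4 of 5 subjects must have completed safety procedures to Day 29.

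Dosing within a cohort is set elsewhere. Section 10.4.1.2 says "In Cohorts 2, 3, and 4, subjects will be dosed at an interval of 24 hours between subjects", and 10.3.1 repeats it. The one review that must take place while a cohort is being dosed is the Day 8 look at the two sentinel subjects in Cohort 1.

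Other provisions bear on an event during dosing:
- 10.1.1: "Subjects will be housed on Day -1, at the time indicated by the CRU, until after the 24-hour blood draw and/or study procedures".
- 11.1.9.2: the investigator or designee evaluates all AEs.
- 11.1.9.4: every SAE, related or not, goes to the sponsor within one working day of the site learning of it.
- 11.1: "Any nonscheduled procedures required for urgent evaluation of safety concerns take precedence over all routine scheduled procedures".
- 10.4.4.2: in an emergency where it appears that "other subjects may be at imminent risk, the blind may be broken for all subjects dosed at that dose level".
- 10.3.4 and 13.2: the study may be terminated by the sponsor, the contract research organisation, the SRC or regulators.

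SAP sections 3 and 4.2 restate the design and add no hold.

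**The concern.** The sponsor already regards one SAE or emergency room visit, whatever its cause, as enough to stop this first-in-human study or lower the dose. The plan does not say that the same event pauses the remaining doses at the level where it happened. Whether the next healthy volunteer is dosed the following day is left to judgement, and no record of a decision to go on is required.

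The dose cannot be taken back. It is a manual push over about 1 to 5 minutes (10.4.1.1). In monkeys, aPTT stayed prolonged to 336 hours at 2 mg/kg and to 672 hours at 10 and 50 mg/kg (8.3.3). Withholding the dose is the surest protection for the next subject.

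**Working it through.** **Inputs.** Cohorts 2–4 have 5 subjects each (4 active, 1 placebo) and Cohort 1 has 6 (4 active, 2 placebo), from 10.3.1. Spacing is 24 hours (10.3.1, 10.4.1.2). Day 29 is 28 days after dosing (672 hours). The escalation review needs 4 of 5 subjects to Day 29 (10.4.1.4).

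**1. The plan's own figure.** 6 + 3 × 5 = 21 subjects, as stated in 10.3.1.

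**2. When the required SRC review falls.** Subject k is dosed k − 1 days after subject 1, so subject 5 is dosed at +4 days. The earliest day on which 4 of 5 can have reached Day 29 is 3 + 28 = +31 days. The only SRC review that must happen for a five-subject cohort therefore comes at least 31 − 4 = 27 days after its last planned dose.

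**3. Planned subjects still undosed if the event is known before the next dose.** The number is 5 − k.

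| Event in subject | Dosed at | Planned subjects still undosed |
|---|---|---|
| 1 | day 0 | 4 |
| 2 | +1 day | 3 |
| 3 | +2 days | 2 |
| 4 | +3 days | 1 |
| 5 | +4 days | 0 |

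If subject 1 was on active drug, the other 4 are 3 active and 1 placebo. If subject 1 was on placebo, all 4 are active. For an event in subject 1, the number left also falls with time: 4 if known within 24 hours, 3 at 24–48 hours, 2 at 48–72, 1 at 72–96, and 0 after that. Replacements, allowed at the sponsor's discretion (10.3.4, numbered under 10.4.3), come on top and may be dosed after +4 days.

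**4. How much of follow-up a hold can reach.** Subject-days before the last planned dose: 4 + 3 + 2 + 1 = 10. Subject-days to Day 29: 5 × 28 = 140. The share is 10/140 = 7.1%. The documents do not say when 3a events are likely, so this measures time, not risk.

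**5. Cohort 1.** After the sentinel review, 6 − 2 = 4 subjects remain (3 active, 1 placebo), also 24 hours apart. An event in the first of these leaves 3.

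**6. Does any mandatory step come before the next dose?** SAE reporting allows one working day. Across a weekend that exceeds 24 hours, so the next dose could precede the report. An emergency room visit that is not an SAE meets 3a but is outside the reporting duty in 11.1.9.4. AE evaluation by the investigator is mandatory, but it is not tied to dosing.

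**The case against.** The strongest reply is that rule 3 already covers this. Section 10.4.1.4 is headed as containing stopping rules, rule 3 carries no time limit, and the Day 29 minimum applies only to going up. Both outcomes under rule 3, stopping or an intermediate dose, are incompatible with carrying on at the current dose. The investigator, the medical monitor and a sponsor representative sit on the SRC, and there is one site. Confinement through the 24-hour procedures means an early event would usually be known before the next dose. The revision history also shows that the 24-hour stagger and the broad form of 3a followed FDA recommendations.

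Much of this stands. An SRC meeting mid-cohort is permitted, rule 3 can be read that way, and a sensible investigator would probably pause. The FDA history does not show whether a hold was considered. What remains is that the trigger, the person who acts and the hold itself are not written. Termination and group unblinding are powers, and the precedence given to urgent evaluation concerns procedures. None of them obliges anyone to withhold the next dose.

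A reader might infer that subjects could go on being dosed with no required review of any kind. The documents do not support that, because evaluation of every AE and reporting of every SAE are mandatory. The gap is the absence of a required hold or SRC review before the next dose.

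**Conclusion.** The point holds in this narrow form and is worth correcting. Followed literally, the protocol allows the next subject in a cohort to be dosed after a 3a event with neither a hold nor an SRC decision.

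The size is at most 4 planned subjects in a five-subject cohort. That maximum needs the event to be in subject 1 and known before the second dose. It assumes dosing exactly 24 hours apart and no replacements.

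Three stronger readings should be resisted:
- That 4 subjects in each of Cohorts 2–4 could add up across the study. Once 3a is met, the determinations listed under rule 3 are to stop or to use an intermediate dose, so the figure applies to one cohort at a time.
- That the protocol forbids an early stop. It does not.
- That nobody in the cohort is left to protect after +4 days. Replacements may still be dosed.

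Nor does the point extend to criterion 3b, the rule on grade 2 or higher AEs in at least 25% of a cohort. A hold on that count, which includes placebo subjects and unrelated events, is a separate trade-off and is not proposed here.

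**What to change.** Add to 10.4.1.4, with cross-references in 10.3.1 and 10.4.1.2, text along these lines:

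> Criterion 3a also applies while a cohort is being dosed, including to replacement subjects. When the investigator learns of a 3a event, further dosing in that cohort is held until the SRC has reviewed the data and documented its decision. If 3a is confirmed, the SRC makes a determination under rule 3 (stop, or an intermediate dose). Dosing at the current level resumes only if the SRC documents that 3a is not met, for example because the exception for extraneous causes applies.

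This wording keeps rule 3's two outcomes and does not add resumption at the same dose once 3a is met. The amendment should also say whether the exception covers emergency room visits. As written it names only SAEs, so a visit for an unrelated minor injury would trigger the hold. The 24-hour interval stays as it is.

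The cost is an amendment approved by the sponsor, the investigator and the IRB (13.8), with no new assessments. Each trigger brings a short delay and an ad hoc SRC review. The documents give no 3a rate, so the frequency has to be assumed. Let q be the chance per subject of a 3a event known before the last dose. With independent subjects and no replacements, a hold occurs in at most 1 − (1 − q)^4 of five-subject cohorts, and at least once over Cohorts 2–4 in at most 1 − (1 − q)^12 of studies:

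| Assumed q | Per cohort | Over Cohorts 2–4 |
|---|---|---|
| 0.5% | 2.0% | 5.8% |
| 1% | 3.9% | 11.4% |
| 2% | 7.8% | 21.5% |

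These are upper bounds, because they give each of the first four subjects the full chance q although the later ones are observed for fewer days before the last dose.
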